4.2 Inclusion criteria

In order to be eligible to participate in this study, a subject must meet all of the following criteria:

- Adult patients with confirmed acute PE, i.e. contrast filling defect in a lobar or more proximal pulmonary artery on computed tomography pulmonary angiography (CTPA), or obstructive shock with echocardiographic confirmed dilatation of the right ventricle and a congested vena cava inferior, both with/without echocardiographic signs of clot in transit or deep vein thrombosis of the leg.
- 2. High risk for mortality, i.e.
 - a. post cardiac arrest (after temporary need for cardiopulmonary resuscitation), OR
 - b. obstructive shock (systolic blood pressure <90 mmHg and signs of end-organ hypoperfusion (e.g. elevated lactate levels >2 mmol/l) or the need for vasopressors (noradrenalin or adrenalin) to maintain an adequate blood pressure), OR
 - c. persistent hypotension (systolic blood pressure <90 mmHg or systolic blood pressure drop ≥40 mmHg for at least 15 minutes) not caused by new onset arrhythmia, hypovolemia, or sepsis, OR
 - d. abnormal RV function on transthoracic echocardiography or CTPA AND elevated cardiac troponin levels AND respiratory failure defined as hypoxemia (SaO2 <90%) refractory to O2 supplementation by nasal cannula or Venturi mask, requiring full face mask O2 supplementation (100% FiO2), high-flow nasal O2, or (non-)invasive mechanical ventilation.
- CDT available and technically feasible so as to allow for a randomization-to-needle time of 60 minutes or less.

4.3 Exclusion criteria

A potential subject who meets any of the following criteria will be excluded from participation in this study:

- "Catastrophic PE", i.e. ongoing cardiac arrest and/or need for extracorporeal cardiopulmonary resuscitation (ECPR) and/or immediate indication for venoarterial extracorporeal membrane oxygenation (VA-ECMO) as judged by the responsible physician(s)
- 2. Glascow Coma Scale <8 following resuscitation for cardiac arrest

- 3. Alternative diagnosis than acute pulmonary embolism contributing largely to the acute hemodynamic and/or respiratory failure, e.g. sepsis, COPD GOLD 3 or 4, or known heart failure with NYHA Functional Classification of 4, as judged by the treating physician.
- 4. A known "do not admit to the ICU" or "do not resuscitate" directive
- 5. An absolute contraindication to systemic thrombolysis, i.e.
 - ✓ History of hemorrhagic stroke
 - ✓ Ischemic stroke in past 6 months
 - ✓ Central nervous system neoplasm
 - Major trauma, major surgery or major head injury in past 3 weeks (note: mild external laceration of the head after, e.g. syncope, does not count as major head injury, especially when a CT scan of the head shows no hematoma)
 - ✓ Active bleeding, life-threatening or into a critically organ/area; OR known severe bleeding diathesis with previous bleeding fulfilling these criteria
- 6. Reperfusion therapy (systemic thrombolysis, surgical thrombectomy or CDT/other catheter directed therapy), or placement of a non-retrieved inferior vena cava filter for acute pulmonary embolism in the past 3 months
- 7. Thrombus in transit through a patent foramen ovale.
- Known chronic thromboembolic pulmonary hypertension (CTEPH), or strong suspicion of CTEPH based on pre-existing clinical findings and combinations of signs of PE chronicity on echocardiography and/or CTPA.^{2,17}
- 9. Known hypersensitivity to systemic thrombolysis, heparin, or to any of the excipients
- 10. If, in the Investigator's opinion, or after consultation with the local PERT-team or EC-members, the patient is not appropriate for thrombectomy
- 11. Chronic use of full-dose oral or parenteral anticoagulation before presentation.
- 12. Pregnancy
- 13. Current participation in another study that would interfere with participation in this study
- 14. Previous enrolment in this study
- 15. Refusal of deferred consent by the next of kin or by the patient himself to use the data. Deferred consent will not be asked to relatives of patients who die in scene, but are included in the study.

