8.4 Withdrawal of individual subjects

Subjects can leave the study at any time for any reason if they wish to do so without any consequences. The investigator can decide to withdraw a subject from the study for urgent medical reasons.

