10. STATISTICAL ANALYSIS

The data will be analyzed on an ITT basis in several steps. The ITT populations consist of all subjects who have been randomized, i.e. when the subject number and allocated regimen are recorded in the eCRF. Patients will be analyzed in accordance with the randomized treatment assignment irrespective of the factual implementation of the assigned treatment regimen. The baseline characteristics in each trial arm will be described. Continuous variables will be described as mean with standard deviation (SD) or median with interquartile range (IQR) for continuous variables depending on their normality of distribution. The Shapiro–Wilk test will be used to assess normality. Categorical variables are presented as numbers and percentages. On top of the ITT analyses a per-protocol (safety population) analysis will be performed. A detailed description of the statistical analysis will be provided in the Statistical Analysis Plan.

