10.2 Secondary study parameter(s)

For continuous secondary endpoints (e.g., DOOR in the first 7 days after randomization), we will estimate mean or median difference between trial arms using an Independent Samples t

Test (mean difference) or a Mann Whitney-U test (median difference), depending on the normality of the distribution. Regarding categorical secondary outcomes, differences between the trial arms will be analyzed using a Chi-square test or Fisher's exact test, when appropriate. Repeated measures secondary outcomes are analyzed using mixed-effects (longitudinal) regression models. Outcomes will be (numerically) stratified according to the type of thrombectomy (FlowTriever vs. Indigo). A per-protocol analysis is performed as a sensitivity analysis. Both R studio and Graphpad software will be used for statistical analysis and making graphs, respectively. A two-sided p-value <0.05 is considered statistically significant. Missing data, where applicable, will be imputed with the use of multiple imputation under the missing-at-random assumption with chained equations. Outcome variables will not be imputed, as is the convention in randomized controlled trials. Patient safety will be monitored by a Data Safety Monitoring Board (DSMB) that will include several senior researchers. Subgroup analyses will be performed (if feasible, i.e. if numbers per subgroup are sufficiently large) for man versus women, age below 75 or 75 and older, different devices used and subtype of high-risk PE.

A cost effectiveness analysis (CEA) will be performed after a time horizon of one year for the primary outcome and QALYs. QALYs will be estimated using the EQ-5D-5L administered at day 7 and after 3, 6, 9 and 12 months, the Dutch tariff, and the "Area under the Curve" approach.^{28,29}

The economic evaluation will be performed in accordance with the 'Dutch Guideline for economic Evaluations'.¹⁸ In the main analysis, the societal perspective will be applied, meaning that all costs will be included irrespective of who pays or benefits (i.e. the cost of the intervention, other healthcare use, informal care, as well as productivity losses from unpaid and paid work). Intervention costs will be micro-costed, all other costs will be measured using cost questionnaires administered at 7 and after 3, 6, 9 and 12 months, and valued using standard prices provided by the 'Dutch Manual for Costing Studies in Health Care'.³⁰

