11.2 Recruitment and consent

Patients will be screened for inclusion upon arrival of the local EXPERT-PE team. The patients eligible for this study are in shock and often respiratory insufficient. Both the study intervention and the systemic thrombolysis are emergency interventions that have to be applied without delay and the intervention fulfils the ethical requirement of clinical equipoise. The study participant can benefit from the intervention, but up to now there is a state of honest, professional uncertainty in the community of expert practitioners as to the effect of the intervention. All in all, the eligible patients have an extremely high risk of dying (up to 70% if left untreated or if appropriate treatment is delayed) and the legal representatives will therefore be in a disturbed mental state complicating an immediate informed decision. The patient will therefore be randomized upon confirmation by the treating physicians that the patients fulfils the criteria of study participation.

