The investigator or treating physician will inform the patient about the study and will ask for deferred proxy consent for use of the study and medical data (deferred consent) immediately if and when the patient is deemed susceptible for this (for the majority of patients, this will be shortly after the reperfusion therapy has been delivered), or the legal representative if the patient remains unable to communicate within 72 hours after randomisation. If the patient has died by that time, the legal representatives will be informed that the patient participated in the study. This can be done either by the local principal investigator or the treating physician, provided that the physician has been explicitly informed of the ethical and legal nuances of the trial. The legal representatives will not be asked for consent to use the data, since: (1) the legal representatives have no independent right on inspection of or say on therapeutic or study data (CCMO: "De nabestaanden hebben geen zelfstandig recht op inzage van de tijdens de behandeling en het onderzoek verkregen gegevens en hebben daar ook geen zeggenschap over. Van toestemming voor het gebruik van de data door de nabestaanden kan daarom ook geen sprake zijn"); (2) possible refusal may cause selection bias and this is ethically unwanted (CCMO: het introduceren van selectiebias door het moeten vragen van toestemming aan de nabestaanden, mocht daar een grond voor zijn, ethisch niet wenselijk is). These patients are essential for the internally validity of the study; 3) the data will be coded. Use of the data has no implications for the patient or legal representatives; and (4) we consider it unethical to burden the grieving relatives with a decision that has no impact on the already performed treatment and only pertains the use of already gathered and coded data.

The legal representatives will be given a letter containing information about the trial. They will also receive an invitation for an appointment with the supervising doctor and an investigator after 6 to 8 weeks, to answer any remaining questions.

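### Exclusion criterion 15 can act only after randomisation, so it removes patients whom the protocol's ITT definition counts

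*Protocol*

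**What the plan says.** Protocol 4.3, repeated in the Summary, introduces its list as reasons to exclude a potential subject from participation. Item 15 of that list is "Refusal of deferred consent by the next of kin or by the patient himself to use the data". The same item keeps patients who die at the scene, whose relatives are not asked.

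Section 11.2 sets the order of events. On enrolment: "The patient will therefore be randomized upon confirmation by the treating physicians that the patients fulfils the criteria of study participation". Consent comes later; of asking the patient it says "for the majority of patients, this will be shortly after the reperfusion therapy has been delivered". The legal representative is approached if the patient cannot communicate within 72 hours of randomisation. For deaths: "If the patient has died by that time, the legal representatives will be informed that the patient participated in the study", and consent is not requested. One reason given is that "possible refusal may cause selection bias and this is ethically unwanted".

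Section 10 then states: "The ITT populations consist of all subjects who have been randomized". Membership is fixed once the subject number and allocation are in the eCRF. Section 10.2 adds: "Outcome variables will not be imputed, as is the convention in randomized controlled trials". Section 8.4 says only: "Subjects can leave the study at any time for any reason if they wish to do so without any consequences". It does not say what happens to the data.

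**The concern.** An eligibility criterion has to be checkable before randomisation. Item 15 is not: nobody can refuse deferred consent before being randomised. For a refuser the protocol therefore gives two incompatible instructions: exclude from participation (4.3), and analyse with all randomised subjects (10).

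The consequence goes beyond wording because retention is uneven. A patient who has died before consent would be sought is always kept. A patient alive at that point can be removed by their own or a representative's refusal, when the arm is known and the early course has been seen. If refusal is related to arm and outcome, the retained groups are no longer the randomised groups. The bias is near zero only if refusal is equal across arms and also unrelated to outcome. The primary result would still be labelled ITT on all randomised subjects.

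**Working it through.** **Passages side by side**

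| Step | Section | Rule |
|---|---|---|
| 1 | 11.2 | Randomise on confirmed eligibility, without prior consent |
| 2 | 3, 11.2 | Open-label treatment, delivered before consent in most patients |
| 3 | 11.2 | Ask deferred consent of those alive; keep those who died |
| 4 | 4.3 item 15 | A refuser is excluded |
| 5 | 10 | ITT is everyone randomised, with no exception |

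Nothing reconciles steps 4 and 5. Section 8.6 covers patients who did not get the allocated treatment, not patients whose data may not be used. Section 10.4 reviews consent and drop-out after 50 patients but does not alter the analysed set.

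**Inputs.** Section 4.4 gives event rates of 0.19 (CDT) and 0.46 (thrombolysis), a difference of 27.5 points and OR 3.71. The printed 0.46 yields 27.0 points and OR (0.46/0.54)/(0.19/0.81) = 3.63. A rate of 0.465 yields 27.5 points and OR 3.705, so 0.465 is used. The sample size is 35 + 70 = 105 analysable. With 5% drop-out, 35/0.95 = 36.8 and 70/0.95 = 73.7, rounded up to 37 + 74 = 111, as printed. All refusal rates below are assumptions.

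**Shift in the expected difference.** Let p be the event rate, d the proportion dying before consent (always kept), r_e the refusal rate among other patients with an event, and r_n the refusal rate among event-free patients. The rate among retained patients is

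q = [d + (1 − r_e)(p − d)] / [d + (1 − r_e)(p − d) + (1 − r_n)(1 − p)].

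Assumed d is 0 to 10% for CDT and 5 to 15% for thrombolysis, 5 points apart. Example, with 10% of event-free patients refusing in both arms: 0.465/0.9465 − 0.19/0.919 = 0.4913 − 0.2067 = 28.5 points.

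| Assumed refusal | Difference among retained (true 27.5) |
|---|---|
| 10% in both arms, unrelated to outcome | 27.5 to 27.8 |
| 10% of event-free patients, both arms | 28.5 |
| 10% of living patients with an event, both arms | 26.5 to 26.8 |
| 10% in one arm only, unrelated to outcome | 26.6 to 28.4 |
| 5% in one arm only, confined to patients with or to patients without an event | 26.4 to 28.8 |

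**Bounds on an observed result.** Suppose all the planned drop-out were refusals: 2 thrombolysis and 4 CDT patients. Their outcomes can fall in 3 × 5 = 15 ways. The p-values are Wald tests from the logistic model of 10.1 (Pearson chi-square in brackets). For 14/35 vs 14/70: OR = (14/21)/(14/56) = 2.67; SE of log OR = √(1/14 + 1/21 + 1/14 + 1/56) = 0.456; z = 0.981/0.456 = 2.15; p = 0.032; 95% CI 1.09 to 6.52.

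| Thrombolysis vs CDT | Difference (points) | p |
|---|---|---|
| **Design-like:** 16/35 vs 13/70 observed | 27.1 | – |
| Six refusers, worst: 16/37 vs 17/74 | 20.3 | 0.030 |
| Six refusers, best: 18/37 vs 13/74 | 31.1 | 0.0009 |
| **Borderline:** 14/35 vs 14/70 observed | 20.0 | 0.032 (0.029) |
| One refuser, thrombolysis without event: 14/36 vs 14/70 | 18.9 | 0.040 (0.037) |
| One refuser, CDT with event: 14/35 vs 15/71 | 18.9 | 0.043 (0.040) |
| Two, both thrombolysis without event: 14/37 vs 14/70 | 17.8 | 0.049 (0.046) |
| Two, one of each: 14/36 vs 15/71 | 17.8 | 0.054 (0.051) |
| Two, both CDT with event: 14/35 vs 16/72 | 17.8 | 0.058 (0.055) |
| Six refusers, worst: 14/37 vs 18/74 | 13.5 | 0.14 |
| Six refusers, best: 16/37 vs 14/74 | 24.3 | 0.008 |

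In the design-like case all 15 combinations stay significant. In the borderline case 6 of 15 lose significance by Wald and 5 of 15 by Pearson; they differ on 14/37 vs 15/74, which gives 0.0501 (0.047).

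**The case against.** The strongest reply is that the effect is small by these very numbers. At the design effect no pattern of refusals within the planned loss changes the conclusion, and the rate scenarios move the difference by little more than one point. Significance is lost only in a constructed borderline result with refusers placed against CDT, and any result at p = 0.032 is that fragile to two lost outcomes of whatever cause. This stands, and it limits the severity.

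Second, refusers leave because permission to use their data is withheld, not because outcomes are not imputed. That also stands. The imputation rule only means that nothing puts them back. The protocol cannot simply analyse those data, so the correction concerns classification, labelling and accounting.

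Third, part of the ground is covered: withdrawal in 8.4, a 5% drop-out allowance in 4.4, monitoring in 10.4, and retention of early deaths in 11.2. Details of sensitivity analyses belong in the SAP, which was not available here, and the consent form, also not seen, may already offer limited consent. This is fair for the details. It does not remove the conflict, because the protocol itself states both rules and a SAP would have to depart from one of them.

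Finally, the selection-bias remark in 11.2 is made about relatives of the deceased. Applying it to living refusers is an inference, though the same reasoning holds for them.

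**Conclusion.** The concern holds. Item 15 cannot work as an eligibility criterion, and it contradicts the ITT definition for every refuser. The refusal rate is unknown, and so is the direction of any bias. The likely effect is modest: under the assumed 5 to 10% refusal patterns the expected difference stays between 26.4 and 28.8 points against 27.5, and a design-like result withstands any outcomes among six refusers. It can matter in a borderline result. There, one refuser does not remove significance in the planned logistic model, but two can if their outcomes are unfavourable to CDT, meaning a CDT refuser with an event or a thrombolysis refuser without one. Even then, two event-free thrombolysis refusers leave p at 0.049. These figures rest on assumed refusal rates, assumed deaths before consent and the inferred rate of 0.465. The point should be corrected, but it does not by itself undermine the trial.

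**What to change.** 1. Take item 15 out of 4.3 and the Summary list, and treat refusal as post-randomisation withdrawal of data, for example in 8.4. Use one rule for the deaths that are kept: item 15 refers to deaths at the scene, 11.2 to any death before consent would be asked.
2. Keep refusers in the randomised count. In section 10, describe the primary set as all randomised patients whose data may be used, and report refusals by arm and timing.
3. Unless the consent form already does so, offer refusers limited consent covering allocated arm, 30-day vital status and primary outcome.
4. Commit to a best-case and worst-case sensitivity analysis over refusers, with the details in the SAP.

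Step 2 corrects the label, step 3 reduces the loss, and step 4 bounds what remains.

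A minor related point: 8.5 can be read as 111 randomised and followed or as 111 completers, while 4.4 gives 111 as recruited including drop-out. State which is meant and whether refusers count towards it. Power is not reduced under either reading.

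The cost is a short wording amendment to 4.3 (and the Summary), 8.4, 8.5 and section 10, notified to the METC under 12.3, possibly one extra option on the consent form, and one sensitivity table. No patients or visits are added if 111 means randomised. If it means completers, 111/0.95 = 116.8, so about 117 would be randomised at 5% loss.

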4.4 Sample size calculation

For the primary endpoint, which is the composite incidence of all-cause mortality and adverse events defined as treatment failure, major bleeding and all-cause stroke at day 30, we calculated the desired sample size largely based on the data from the FLAME prospective registry.¹³ This study used a somewhat different composite primary endpoint of all-cause mortality, bailout to alternative thrombus removal strategy, clinical deterioration and major Version 2.1: 16-12-2024 19 of 38

bleeding. These endpoints were however not well enough defined and the clinically important endpoint of stroke was not a component of the primary outcome. We can however basically state that "bailout" and "clinical deterioration" may match our proposed component of treatment failure. The primary endpoint in FLAME occurred in 17.0% and in 63.9% (AR difference 46.9%) in the FlowTriever and context arms, respectively. Including ischemic stroke, the event rates were 18.9% and 67.2% (AR difference 48.3%), respectively. This study suffered from selection bias and confounding by indication, and therefore the treatment effect is likely overestimated. Patients were enrolled in the FlowTriever arm in the years 2021 and 2022 where event rates in the Context arm were obtained from historical data (years 2010-2020) derived from a meta-analysis.

To assess statistical power, the probability of the primary outcome was assumed to be 0.19 in the thrombectomy arm (based on the most recent data available) and 0.46 in the systemic thrombolysis arm (corresponding with a treatment OR of 3.71 and a risk difference of 27.5%; number needed to treat 3.6). The minimum clinically important difference was set at 27.5% based on discussion within the project group, scientific societies and patient representatives, and on clinical relevance for the difference facets of the composite endpoints. The assumed ARR of 27.5% consists of 5% decrease in mortality, 21.5% reduction in treatment failure or major bleeding and 1% reduction in ischemic stroke (the latter both based on expert opinion).¹⁸ Given a power of 80%, a two-sided α -level of 5%, and a 1:2 (systemic thrombolysis:CDT) patient allocation, 35 patients are needed in the systemic thrombolysis and 70 patients in the CDT arm. Assuming 5% drop-out, 37 patients (systemic thrombolysis) and 74 patients (CDT; total 111 patients) will be recruited. The calculation was done using G*Power (version 3.1.9.6) and is based on proportion difference tested with an anticipated OR.

5. TREATMENT OF SUBJECTS

5.1 Investigational product/treatment

The standard of care for the patients eligible for the TORPEDO-NL trial is parenteral anticoagulation and systemic thrombolysis (Actilyse® [manufactured by Boehringer Ingelheim Pharmaceuticals, Inc., Ingelheim am Rhein, Germany] 10mg bolus followed by 90mg in two hours). The intervention consists of parenteral anticoagulation and immediate CDT (FlowTriever or Indigo) without systemic or locally administered systemic thrombolysis. Thrombectomy is performed according to the IFU for the particular device and occurs via echoguided femoral or jugular venous access by an interventional cardiologist, interventional radiologist or vascular surgeon. The catheter is advanced over a preplaced guidewire across the right heart into the pulmonary arteries to the location of proximal thrombus. After removal

of the dilator, the thrombus is extracted by controlled volume aspiration through an aspiration catheter using either a syringe or the dedicated aspiration system depending on the device of choise, with multiple aspirations performed as needed. Investigators will determine when to terminate the procedure based on their assessment patients respiratory and hemodynamic status. Procedural objectives will be clearly stated prior to the intervention and respiratory and hemodynamic parameters, including pulmonary artery pressures, will be evaluated pre- and post-thrombectomy per protocol to inform each operator's decision to determine completion. Revaluation of the patient's condition should be carried out using blood loss as a reference, establishing 400 cc of blood loss as a cut-off value. The type and dosage of anticoagulant prescribed to each patient at discharge will be determined by local practice but administration will initially be parenteral for at least 24h after randomization. Participating centres have an institutionalized multidisciplinary Pulmonary Embolism Response Team (PERT) or EXPERT-PE team in place. The intervention team should have ample experience with endovascular interventions. At least one member of the intervention team should have sufficient experience with thrombectomy for PE and should have completed at least 3 full procedures (logged) with one of the devices. Procedures that have been carried out by two team members (for example, in a training setting) do count.

